2. HYPOTHESIS AND OBJECTIVES

Primary objective will be to examine the proportion of patients triaged to the low risk WMC clinics after brief intervention by a nurse coordination and completion of 4 sessions of Kurbo Program over a 12 month recruitment period.

Secondary objectives:

1. To examine the effect of the waitlist intervention and WMC intervention on mean BMI z-score change at 3 months and 6 months.
2. To examine the feasibility of using Kurbo program as a waitlist intervention for the target population as measured by quantifying the percentage of patients offered the program who agreed to enrol.
3. To examine program fidelity as measured by the percentage of patients who complete each of the 12 sessions of online coaching by Kurbo coaches
4. To examine changes in treatment outcomes as a function of program fidelity as measured by those who complete more online coaching show greater improvements in BMI z-score
5. To examine other factors that predict poor response (parental BMI, quality of life, disordered eating and physical activity measurement) in high risk WMC
6. To examine the effects of waitlist intervention on lifestyle changes (nutrition and physical activity), quality of life and disordered eating at 3 and 6 months.
7. To examine the rate of attrition from WMC after implementation of the waitlist intervention and new model of care in WMC.
8. Examine changes in branched chain amino acid(BCAA), aromatic amino acid (AAA) and long chain acylcarnitines, insulin and second hour glucose results and fasting lipids at baseline and at month 6.

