5. STUDY DESIGN AND PROCEDURES/METHODOLOGY

Children aged 10-17 years old with BMI percentile of above 90th percentile, who are referred to the WMC, will receive a brief intervention by the WMC nurse coordinator followed by introduction to Kurbo program for more detailed dietary and physical activity recommendations and implementation of behavioural changes. The patient's progress will be reviewed by the nurse clinician at one month post intervention to determine whether the BMI percentile has shown a reduction through the Kurbo Program. Patients that declined Kurbo intervention, has a BMI of more than 99th percentile or continue to have increase in their BMI percentile in Kurbo program, will be offered the high risk weight management clinic appointment for a more detailed multidisciplinary evaluation for targeted intervention. Patients that are able to engage with Kurbo intervention and showed a decrease in BMI percentile over 4 sessions of Kurbo will be offered the low risk weight management clinic.

The following section illustrates how and when the outcomes will be measured. Figure 1 depicts the flow diagram for an adolescent at the point of referral to the WMC.

Figure 1: Flow diagram of the intervention at the point of referral to WMC

Study visits and procedures

The expected duration of study involvement for each participant will be 6 months with 5 in-person visits with the study team. Table 1 depicts the study visits and measurements for each visit.

Table 1: Study visits and measurements

	Baseline	Visit 1	Visit 2	Visit 3	Visit 4	Visit 5
Parental demographics and parental BMI	x					
Anthropometry (weight, height, waist circumference, blood pressure and body fat composition)	x		x	x		x
Peds QL questionnaire	x			x		x
Three day food diary	x			x		x
Eating Pattern Inventory	x			x		x
Evaluation questionnaire				x		
Accelerometry	x			x	x	
Fasting insulin, lipids, oral glucose tolerance test		x			x	
Plasma amino acid, long chain acylcarnitine levels and vitamin D level, calcium, magnesium, phosphate and alkaline phosphatase		x			x	

First contact (Baseline):

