Prior to the clinic visit, the nurse coordinator or clinical research coordinator will obtain a summary of the adolescent's progress in Kurbo to aid the discussion during the clinic visit. If there has been no change in the adolescent's BMI percentile after 4 sessions of Kurbo program or the adolescent had not signed up for Kurbo, the adolescent will be placed in the high risk clinic. If the adolescent had shown reduction in BMI percentile after 4 sessions of Kurbo, they will be placed in the low risk clinic. There are several key objectives to the visit. Firstly, it is to objectively measure the patient's weight and height, body fat composition, waist circumference and blood pressure. In the low risk clinic, the current clinic slots are in 15 minutes slot as the main purpose of the consult is to screen for obesity related co-morbidities and for motivational interviewing. The visit also allows the nurse coordinator to build further rapport with the adolescent. In the high risk clinic, the clinic slots are in 30 minutes slot to allow for more time to obtain a medical and psychosocial history. The weight management program for high risk and low risk WMC will be as routine care.

Current low risk WMC patients will be offered 2 monthly follow up with optional dietitian and exercise physiologists counselling and exercise sessions. The high risk WMC patients will be routinely offered the standard high risk follow up protocol consisting of weekly follow up with the multidisciplinary team for 4 weeks followed by 2 weekly appointments for 2 months and monthly appointment thereafter based on clinical response.

Visit 3:(12-23 weeks)

Prior to the clinic visit, the nurse coordinator or clinical research coordinator will obtain a summary of the adolescent's progress in Kurbo to aid the discussion during the clinic visit. The follow up will be timed together with the WMC appointment to measure the patient's weight and height, body fat composition, waist circumference and blood pressure as well as administration of the questionnaire. Accelerometers may also be fitted or returned to

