8.2. Statistical and Analytical Plans

Data will be analysed using SAS version 9.3 for Windows (SAS, Inc., Cary, NC USA). BMI will be calculated as kg/m² and BMI-z score calculated using the L, M, S parameters published by the CDC. (34) Baseline demographic, anthropometric measurements, parental BMI, quality of life measurement, disordered eating and physical activity were compared between those in low risk WMC versus those in high risk WMC using the Wilcoxon rank-sum test and the two-sample-t-test for non-normal and normal continuous variables, respectively, and the Fisher's exact test for categorical variables. Changes in cardiometabolic risk factors between first visit and at month 12 will be compared using the paired-sample t-test. Generalized linear mixed model will be carried out on the BMI z-score over multiple visits over 12 month follow up period. The mean value of BMI z-score is considered as a function of time from the baseline. The variance components is used as the covariance structure in generalized linear mixed model. It models a different variance component for each random intercept to allow each child to have his/her own overall level of BMI z-score after taking into account baseline covariate. A time-group interaction will be included to test whether the rate of change of BMI z-score is different between adolescents in low risk and high risk WMC.

There is no reason to assume that this project will lead to an excess of adverse events as the waitlist intervention consists of advice from the nurse and offer of referral to a Kurbo program, neither of which seem likely to create harm. Nonetheless, there are several safety net in place for the waitlist intervention. Firstly, as part of standard Kurbo procedures, any excessive weight loss or weight gain will prompt the Kurbo coaches to inform parents to seek help from their GP and the WMC nurse coordinator will be informed if any concerns arise. Secondly, the WMC nurse coordinator will have administrative rights to Kurbo program and will be able to monitor patient's weight data and communication with Kurbo coaches and will highlight any concerns that arise as a result of intervention. There will also be a feedback form (A month 3 evaluation) administered by the clinical research coordinator on the participants' attitudes to the waitlist intervention and to identify any adverse events at the first WMC visit. As this is a pilot study, there will be no interim analyses.

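### The only analysis using objective 5's factors compares low with high risk clinic members: it mixes severity and uptake with early response and leaves response within the high risk clinic unexamined

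*Combined protocol and SAP*

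**What the plan says.** Section 2, secondary objective 5, is: "To examine other factors that predict poor response (parental BMI, quality of life, disordered eating and physical activity measurement) in high risk WMC".

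Section 8.2 names the same factors in one place. Together with demographics and anthropometry, their baseline values "were compared between those in low risk WMC versus those in high risk WMC", by rank-sum or t-test for continuous variables and Fisher's exact test for categorical ones. No adjustment is mentioned.

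Section 8.2 has two further analyses. A mixed model of BMI z-score contrasts the two clinics: "A time-group interaction will be included to test whether the rate of change of BMI z-score is different between adolescents in low risk", as against the other clinic. It takes in a baseline covariate that is not named and lets each child "to have his/her own overall level of BMI z-score after taking into account baseline covariate". Paired t-tests cover change in cardiometabolic risk factors.

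Clinic placement is described twice in section 5. The opening paragraph offers a high risk appointment to these children: "Patients that declined Kurbo intervention, has a BMI of more than 99th percentile or continue to have increase in their BMI percentile". Those who engaged with Kurbo and "showed a decrease in BMI percentile over 4 sessions of Kurbo will be offered the low risk weight management clinic". The Visit 2 text covers a child with no change in percentile or no Kurbo enrolment: "BMI percentile after 4 sessions of Kurbo program or the adolescent had not signed up for Kurbo, the adolescent will be placed in the high" (the sentence ends by naming that clinic). It does not mention the 99th percentile. Section 1 treats severe obesity as a filter of its own, so that only early responders who are not severely obese go to low risk care.

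**The concern.** The objective needs an outcome (response) and a population (children in the high risk clinic). The planned test has neither. Its grouping variable is clinic membership, which is settled at about Visit 2, before any response to high risk care can be seen. Membership also depends on more than early response: under section 1 and the opening of section 5, a child above the 99th percentile who responds well is still placed in the high risk clinic.

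Two errors can follow. A factor correlated with baseline severity, but not with response, may be reported as a predictor of poor response. A factor that does predict poor response may be missed, either because the high risk group is a mixture or because the response in question comes after placement.

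**Working it through.** **1. Match the objective to the planned analyses.**
- Clinic comparison: uses the named factors, but has no response variable and nothing within a clinic.
- Mixed model: has BMI z-score over time, but only a time-by-clinic term. No term lets a named factor alter the rate of change.
- Paired t-tests: concern cardiometabolic change only.

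No analysis relates a baseline factor to outcome among high risk clinic members.

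**2. Inputs for the dilution.** The sample is 45 (section 4.1). The documents give neither the share above the 99th percentile nor the share not signing up, so the following are assumptions: a = 0.20-0.40 above the 99th percentile; d = 0.05-0.15 not signed up; r = 0.30-0.50 non-response. Section 1 cites early response of 60-80%, which would put r at 0.20-0.40; this is used as a sensitivity range.

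**3. Size of the high risk group.** H = 45 × [(a + d) + (1 − a − d) × r].
- Smallest: a = 0.20, d = 0.05, r = 0.30: 45 × 0.475 = 21.
- Largest: a = 0.40, d = 0.15, r = 0.50: 45 × 0.775 = 35.

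**4. Share of the group that are non-responders.**

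*Counting only children at or below the 99th percentile:* share = (1 − a − d) × r / [(a + d) + (1 − a − d) × r].
- a = 0.40, d = 0.15, r = 0.30: 0.135 / 0.685 = 0.20 (6 children).
- a = 0.20, d = 0.05, r = 0.50: 0.375 / 0.625 = 0.60 (17 children).

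*Letting severe children fail to respond at the same rate:* share = (1 − d) × r / [(a + d) + (1 − a − d) × r].
- Same low corner: 0.255 / 0.685 = 0.37.
- Same high corner: 0.475 / 0.625 = 0.76.

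**5. Effect on a true difference.** Suppose non-responders and responders differ by 0.8 SD, and the remaining high risk children resemble responders. The low risk clinic holds only responders, so the clinic difference is 0.8 × share.
- First count: 0.8 × 0.20 = 0.16 to 0.8 × 0.60 = 0.48 SD.
- Second count: 0.8 × 0.37 = 0.30 to 0.8 × 0.76 = 0.61 SD.

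With r = 0.20-0.40 instead:
- First count: 0.09 / 0.64 = 0.14 to 0.30 / 0.55 = 0.55, or 0.11-0.44 SD.
- Second count: 0.17 / 0.64 = 0.27 to 0.38 / 0.55 = 0.69, or 0.21-0.55 SD.

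**6. If the Visit 2 wording is the rule used.** Severity is then no route, and share = (1 − d) × r / [d + (1 − d) × r]. With r = 0.30-0.50 this runs from 0.255 / 0.405 = 0.63 to 0.475 / 0.525 = 0.90, or 0.50-0.72 SD. With no decliners the share is 1 and this dilution disappears.

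**7. What the planned t-test would flag.** A simulation used 45 children, 4,000 repetitions per scenario, 60-80% early response, an assumed 20-60% above the 99th percentile, no decliners, a two-sided 5% test, and severity, early response and later response drawn independently.
- Factor correlated 0.5 with severity only: significant in 20-62% of trials.
- Factor correlated 0.5 with early non-response only: 11-55%, falling as the severe share grows.
- Factor correlated 0.5 with later response only: about 5%, the false-positive rate. A correlation within the high risk clinic finds it in 54-88%, with complete follow-up.

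**8. What a within-clinic analysis can support.** Under step 7's inputs, the high risk clinic has 45 × [1 − 0.8 × 0.8] = 16 to 45 × [1 − 0.6 × 0.4] = 34 children. With 80% power at a two-sided 5% level, the smallest detectable correlation is about 0.62 at 18 children, 0.57 at 22 and 0.46 at 34.

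**The case against.** **Poor response may simply mean placement in the high risk clinic.** Section 8.2 repeats the objective's list of factors, and section 1 describes high risk obesity as poor response to earlier stages or BMI above the 99th percentile. On that reading the comparison does address objective 5, loosely. This is plausible, but it does not rescue the test: several routes into the clinic are pooled and baseline BMI is not adjusted for. The objective seeks further factors, while section 1 already links severe obesity to poor response, so the analysis has to separate the two.

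**The dilution may be small.** The Visit 2 text omits the 99th percentile, and section 8.1 speaks of 45 adolescents enrolled into Kurbo, so decliners may lie largely outside the sample. This stands as a limit on the size (step 6). It does not supply the missing analysis within the high risk clinic.

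**Two stronger readings are tempting and are not supported.** A reader might infer that the comparison does little more than return the sorting rule, so that anything related to BMI will emerge as a predictor. That fits anthropometry, but the four named factors are not sorting variables. Even at a correlation of 0.5 with severity, a factor is flagged in 20-62% of simulated trials, and the comparison retains some information on early response. A reader might also take 20-60% as the true share of non-responders. It is a worst case, because it counts no child above the 99th percentile as failing to respond, contrary to what section 1 says of severe obesity.

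**The better analysis will be imprecise.** This is true. The clinic's audit in section 1 reports 58% dropout after the initial visit, accelerometry is optional, missed assessments are excluded, and Visit 5 height and weight may be self-reported.

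**Conclusion.** The concern holds in a limited form. Followed exactly, section 8.2 leaves response within the high risk clinic unanalysed and gives only an unadjusted clinic contrast in which severity and uptake are mixed with early response. That gap rests on the text alone and does not depend on any assumed figure.

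The size of the dilution does depend on assumptions. Under the opening of section 5, a true 0.8 SD difference would appear as roughly 0.16-0.61 SD, given the assumed ranges for a, d and r and given that the other high risk children resemble responders. Under the Visit 2 wording the loss is smaller. The simulated rates also assume that later response is independent of early response. Section 1 cites evidence that early loss predicts long-term loss, so the comparison may say something indirectly about later response.

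This is a secondary objective in a pilot without a sample size calculation. It should be settled before analysis, but it does not affect the primary objective.

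**What to change.** 1. Keep the low-versus-high comparison as a description of the two clinics, and tabulate the reason for each high risk placement.
2. Reconcile the two placement texts in section 5 on the 99th percentile and on a rising versus an unchanged BMI percentile, so that the groups are defined once.
3. For objective 5, define response in the high risk clinic as BMI z-score at Visit 5 given Visit 2. Regress Visit 5 BMI z-score on one baseline factor at a time, adjusting for the Visit 2 value, and for placement reason only if numbers allow.
4. As a separate analysis of early response, compare baseline factors between Kurbo starters with and without a measured fall in BMI percentile by Visit 2, adjusting for baseline BMI z-score.
5. Report estimates with confidence intervals, label both analyses exploratory, and state the number of children contributing to each factor.

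The cost is a revision of the analysis text. Table 1 already schedules the factors at baseline and anthropometry at baseline and Visits 2, 3 and 5; the reason for placement has to be recorded. The price is small groups, gaps where measurements are optional, and wide intervals.

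### Section 8.2 analyses outcomes at month 12, but the timed objectives end at month 6 and the last scheduled assessments fall in weeks 24-36

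*Combined protocol and SAP*

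**What the plan says.** Two consecutive sentences of section 8.2 set the time frame of the longitudinal analyses. For cardiometabolic outcomes: "Changes in cardiometabolic risk factors between first visit and at month 12 will be compared using the paired-sample t-test". For weight: "Generalized linear mixed model will be carried out on the BMI z-score over multiple visits over 12 month follow up period".

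The rest of the plan uses a shorter time frame.

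- **Section 2, secondary objective 1** concerns "mean BMI z-score change at 3 months and 6 months".
- **Secondary objective 6** covers lifestyle changes, "quality of life and disordered eating at 3 and 6 months".
- **Secondary objective 8** opens "Examine changes in branched chain amino acid(BCAA), aromatic amino acid (AAA) and long chain acylcarnitines" and continues with "insulin and second hour glucose results and fasting lipids at baseline and at month 6".
- **Section 5, study visits:** "The expected duration of study involvement for each participant will be 6 months with 5 in-person visits with the study team".
- **Section 5, Table 1** has six columns, baseline and Visits 1 to 5. The row "Anthropometry (weight, height, waist circumference, blood pressure and body fat composition") is marked at baseline and Visits 2, 3 and 5. The blood-test rows are marked at Visits 1 and 4 only.
- **Section 5, visit descriptions and visit list** place Visit 3 in weeks 12-23 and Visits 4 and 5 in weeks 24-36. A patient who comes back for Visit 5 after that window is counted as lost to follow-up.

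**The concern.** Section 8.2 is the only place that says how the data will be analysed, and it names a time point that the schedule does not deliver. The paired t-test needs a second value at month 12, and no visit is planned to provide one. It is also the only method named for cardiometabolic change, so objective 8 has no analysis that can be run as written.

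The mixed model is in a milder position. It can be fitted to whatever scheduled visits exist, but the follow-up it claims is longer than the follow-up planned.

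Two further details of the t-test are open. Section 8.2 does not list the cardiometabolic risk factors: objective 8 names blood markers, while blood pressure, waist circumference and body fat are measured but not assigned to any test of change. The first visit is also ambiguous, because anthropometry starts at baseline and bloods start at Visit 1.

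The stakes are limited. These are secondary objectives of a pilot, and the primary objective (the proportion triaged to the low risk clinic) does not use either analysis. The risk that someone picks the endpoint time after seeing the data is small, because the objectives already fix it.

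**Working it through.** No power or sample-size formula applies. The check converts the visit windows to months and compares them with month 12.

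**Inputs:** month 12 (section 8.2); months 3 and 6 (section 2); Visit 3 in weeks 12-23 and Visits 4 and 5 in weeks 24-36 (section 5). The protocol does not define a month, so two conventions are used: a calendar month of 365.25 / 12 / 7 = 4.348 weeks, and a four-week month.

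| Quantity | Calendar months | Four-week months |
|---|---|---|
| Month 12 in weeks | 12 × 4.348 = 52.2 | 12 × 4 = 48 |
| Opening of last window, week 24 | 24 / 4.348 = month 5.5 | 24 / 4 = month 6.0 |
| Close of last window, week 36 | 36 / 4.348 = month 8.3 | 36 / 4 = month 9.0 |
| Gap from week 36 to month 12 | 52.2 − 36 = 16.2 weeks (3.7 months) | 48 − 36 = 12 weeks (3 months) |
| Month 3 in weeks | 13.0, inside weeks 12-23 | 12, inside weeks 12-23 |
| Month 6 in weeks | 26.1, inside weeks 24-36 | 24, inside weeks 24-36 |

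The month-12 figure cannot be obtained from the schedule under either convention: 0 of the 6 assessment points in Table 1 reach it. Months 3 and 6 fall inside the Visit 3 and Visit 4/5 windows under both conventions, so the schedule fits the objectives and not section 8.2.

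**Measures that depend on the t-test.** From objective 8 and the blood-test description in section 5:

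- metabolites: 3 BCAA + 2 AAA + 10 acylcarnitines = 15
- insulin 1, 2-hour glucose 1, lipids 4 (triglycerides, total cholesterol, HDL-C, LDL-C) = 6
- total: 15 + 6 = 21

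This is an upper limit for two reasons. Objective 8 refers to long chain acylcarnitines, whereas section 5 lists 10 acylcarnitines in all. Section 8.2 also does not say that the amino acids and acylcarnitines count as cardiometabolic risk factors. If none of the metabolites counts, 6 measures depend on the t-test, and the other 15 have no named test of change at all.

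Blood tests are optional, and section 5 removes a patient from the analysis of any assessment that was missed. Each measure may therefore have fewer complete pairs than the 45 planned patients.

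**The case against.** The best alternative reading concerns the BMI model. Section 8.2 speaks of multiple visits without limiting them to study visits. Section 5 says that trained staff measure anthropometry and blood pressure at each clinic visit, and routine follow-up is offered every two months in the low risk clinic and eventually monthly in the high risk clinic. BMI values after week 36 could therefore exist in clinic records, and the authors may have meant to use them. This is a reason to ask what was intended, but it does not remove the conflict. Those appointments are routine care and not study assessments, study involvement is 6 months, late returns for Visit 5 count as lost, and routine follow-up supplies no scheduled month-12 bloods.

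Four smaller points:

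- The primary objective mentions 12 months, but as a recruitment period. Section 8.2 refers to time within a patient, so accrual does not explain the figure.
- The size of the gap depends on the month convention. This stands, and the range of 12 to 16.2 weeks is the fair statement.
- Objectives 2 to 5 and 7 give no calendar time. This also stands: the month-6 limit applies to the objectives that state an assessment time (1, 6 and 8).
- The count of 21 measures assumes a wide meaning of cardiometabolic. This stands as a caveat, and the count is an upper limit.

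**Conclusion.** The concern holds. Section 8.2 specifies a month-12 comparison and a 12-month model horizon, while the timed objectives, the participation period and the visit windows all agree on month 6. The last window closes 12 weeks (four-week months) to 16.2 weeks (calendar months) before month 12. The paired t-test cannot be run as written on scheduled data. The mixed model can be run, and only its stated follow-up needs reconciling.

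The conclusion rests on the visit schedule in section 5 being complete. Table 1, the visit descriptions and the visit list all end at Visit 5, so there is no sign of a missing later visit. It does not depend on the month convention or on how many measures count as cardiometabolic. The point should be fixed, but it is not critical: it affects secondary objectives only, and the primary objective is untouched.

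**What to change.** If the 6-month objectives stand, amend section 8.2 as follows.

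1. Replace month 12 in the t-test sentence with the month-6 assessment (weeks 24-36). Pair Visit 1 with Visit 4 for the objective 8 blood markers, and for HbA1c if it is meant to be included.
2. List the cardiometabolic risk factors. If blood pressure, waist circumference and body fat are among them, pair baseline with Visit 5 for these.
3. Replace the 12-month follow-up of the mixed model with the scheduled anthropometry visits: baseline and Visits 2, 3 and 5. Keep the existing time-from-baseline term, and report the model-estimated mean change in BMI z-score with a 95% CI at 3 and 6 months, which answers objective 1 directly.
4. As useful additions, report the number of complete pairs for each blood measure, and state how many Visit 3 and Visit 5 BMI values rest on the self-reported height and weight that section 5 allows when a visit is missed.

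This is a wording change with no new visits, measurements or patients. If routine-clinic BMI values were meant to enter the model, section 8.2 should say so and give the cut-off time. If a month-12 assessment was really intended, the objectives, the participation period and the visit schedule have to be reconciled with section 8.2, which is a larger amendment.
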